CheckMate 204 is a Phase II trial for melanoma patients with > 1 measurable, non-irradiated melanoma brain metastases (MBM) 0.5–3.0cm. Asymptomatic patients not on steroids or anti-epileptics are treated with nivolumab 1 mg/kg + ipilimumab 3 mg/kg, then nivolumab maintenance. The intracranial clinical benefit rate (CBR; proportion of patients with complete response + partial response + stable disease) is 29% (n = 101), with 26% partial response and 4% stable disease ⁵⁹. Toxicity was similar to nivolumab + ipilimumab in non-brain metastatic patients. An amendment added an exploratory cohort of symptomatic patients on steroids (n = 20). For symptomatic patients (n = 18) the intracranial overall response rate was 16.7% and CBR was only 22% ⁶⁰.

Anti-PD1 Brain Collaboration (ABC) was a phase II trial for melanoma patients with active brain metastases, including patients that had previously received targeted therapy with *BRAF* and MEK inhibitors. When patients with asymptomatic untreated brain metastases received combined ipilimumab and nivolumab as their first therapy, 56% (15/27) achieved

an intracranial response and 19% (5/27) achieved a CR³⁷. No new or unexpected toxicities were associated with drug therapy in this study.

1.1.3.2 *Elevated Liver Enzymes and Bulky Disease*

A meta-analysis of 617 *BRAF* mutant melanoma patients randomly assigned to dabrafenib + trametinib in BRF11320, COMBI-d, and COMBI-v was subjected to regression tree analysis to identify prognostic factors for response to therapy³⁶. Four prognostic groups of baseline factors were identified to predict progression free survival: normal LDH with less than 3 sites of metastases, normal LDH with more than 3 sites of metastases, LDH up to 2x upper limit of normal (ULN), and LDH > 2x ULN. Normal LDH with less than 3 sites of metastases had the longest 1-year PFS and (68%) and OS (90%) (n = 237). Overall response was seen in 65% (60/93) with LDH concentration of one to two times ULN and ECOG of 0; 48% (27/56) with LDH concentration of one to two times ULN and ECOG of 1; and 50% (35/70) with LDH concentration at least two times the ULN.

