8.3 Sample Size Considerations

Twelve patients will be evaluated in each phase I cohort; 30 patients will be evaluated for clinical response and clinical benefit in each phase II cohort. The total enrollment, in the absence of early stopping, is 84 patients (24 phase I / 60 phase II). Inference regarding safety of each cohort will depend upon the proportion of patients with DLT. An upper 90% confidence bound on these estimates can be used as a “rule out” criteria by the investigator such that any an unacceptably high DLT rate that is greater than the upper confidence interval may be ruled out.

Table 8.1 Upper Confidence Bounds for DLT Rate

Number of DLTs Among 12 Treated	Upper Bound of 90% Confidence Interval (%)
0	17
1	29
2	39
3	48
4	56
5	64
6	71
7	78
8	85
9	90
10	95
11	99
12	100

For example (see table 8.1), if none of 12 patients have a DLT one could claim the DLT rate is no higher than 17%, If 6 of 12 patients have treatment-related DLT the upper confidence bound is 71%, that is, the observed data (6/12) is consistent with a rate up to but not higher 71% . thus, one can rule out a DLT rate of 72% or greater.

Phase II cohorts will be used to (1) further refine the safety profile by re-estimating the DLT rate and (2) providing a preliminary estimate of efficacy.

While the phase II cohorts are accruing, The DLT rate will be continuously monitored and the trial will be suspended if the DLT rate appears to be too high. We assume, a priori, the DLT rate is thought to be 50%. A continuous monitoring program will be implemented to

detect if this assumption is an underestimate such that the rate were actually 60% or higher. Beginning with the 5th patient, continuous Bayesian monitoring calculates the probability that the DLT rate is too high and provides a stopping rule. We assume a prior

DLT probability of 50% and that the prior probability has a beta distribution with parameters 1.5 and 1.5, producing a mean of .5. As each evaluable patient is evaluated for DLT, accumulated data is used to derive the posterior probability. If the posterior probability of a DLT rate of 60% is 50% or greater, the stopping rule in the table is triggered.

The following tables provides rules for suspending the trial if the actual rate is as high as 60%:

Table 8.2 DLTs Triggering Trial Suspension at 60%

Number of Evaluable Patients (Inclusive)	Suspend if there are This many DLTs	Number of Evaluable Patients (Inclusive)	Suspend if there are This many DLTs
0-4	-----	17	11

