5-6	4	18-19	12
7	5	20-21	13
8-9	6	22	14
12	8	23-24	15
13-14	9	25-26	16
15-16	10		

For example, if 6 DLTs are observed among the first 9 patients the stopping rule for 60% DLT is enacted to signal trial suspension. The accumulated toxicities will then be evaluated by the Data and Safety Monitoring Committee for further action.

Inference from a complete 30 patient expansion cohort.

If either of the expansion cohorts runs to completion without stopping due to excess toxicity, confidence intervals can be used for inference. First, to rule out excess toxicity, an upper 90% one-sided confidence intervals (table 8.3) provides an upper bound to the DLT rate (analogous to the phase I approach). Secondly, a lower 80% one-sided confidence bound (table 8.4) can be used to rule out an ineffective regimen. (A narrower, 80% bound is used here since we want a decision that is only suggestive rather than definitive).

Table 8.3 Upper Confidence Bounds for DLT Rate

Table 8.4 Lower Confidence Bounds for Response

Number of DLTs Among 30 Treated	Upper Bound of 90% Confidence Interval (%)
0	7%
1	12%
2	17%
3	21%
4	25%
5	29%
6	32%
7	36%
8	40%
9	43%

10	46%
11	50%
12	53%
13	57%
14	60%
15	63%

Operating characteristics of possible decision rules in phase II

If a 30-patient phase II cohort is completed the following decisions are possible:

If 23 or more DLTs are observed among 30 patients the combination can be considered as too toxic and a DLT rate of 75% or greater cannot be ruled out. The probability of 23 or more DLTs with a 75% DLT rate is 92%. If the actual rate is 40% or less, the probability of 14 or fewer DLTs is 82%

Number of Responses Among 30 Treated	Lower Bound of 80% Confidence Interval (%)
0	0%
1	0%
2	3%
3	5%
4	8%
5	10%
6	13%
7	16%
8	19%
9	22%
10	25%
11	28%
12	31%

Considering a preliminary assessment of efficacy, three or fewer objective responses will suggest lack of efficacy with a response rate no better than 5%. The probability of observing 3 or fewer responses when the actual rate is 5% is 94%. However, if the actual response rate is 20% the probability of 4 or more responses is 87%.

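### Section 8.3 reads three or fewer responses of 30 as a rate of at most 5%, but that is an upper-limit claim resting on a lower bound; 3/30 is compatible with rates up to about 18–21%

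*Combined protocol and SAP*

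**What the plan says.** Section 8.3 plans that "30 patients will be evaluated for clinical response and clinical benefit in each phase II cohort". For a completed cohort, "a lower 80% one-sided confidence bound (table 8.4) can be used to rule out an ineffective regimen", and the level is explained: "A narrower, 80% bound is used here since we want a decision that is only suggestive rather than definitive". Table 8.4 lists this bound for 0 to 12 responses of 30 and prints 5% at 3.

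The decision sentence follows: "three or fewer objective responses will suggest lack of efficacy with a response rate no better than 5" percent. Two operating characteristics support it: "The probability of observing 3 or fewer responses when the actual rate is 5% is 94" percent, and "if the actual response rate is 20% the probability of 4 or more responses is 87" percent. No reason is given for choosing 5% or 20%.

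The background sections report response rates in patients close to the two phase II groups.

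- **Symptomatic brain metastases (1.1.3.1).** For nivolumab plus ipilimumab: "For symptomatic patients (n = 18) the intracranial overall response rate was 16.7% and CBR was only 22" percent. For BRAF plus MEK inhibition the cited intracranial response rate is 59% (n = 17).
- **Elevated LDH on BRAF plus MEK inhibition (1.1.3.2).** 65% (60/93) and 48% (27/56) in the two strata with LDH at one to two times the upper limit of normal, and "50% (35/70) with LDH concentration at least two times the ULN".

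**The concern.** A statement that the rate is no better than some value needs an upper bound. The efficacy bound in the plan is a lower one. At the cut-off itself, the observed rate is twice the figure that the regimen is said not to exceed.

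The plan reads bounds the right way round for safety: in phase I, none of 12 patients with a DLT is taken to mean a rate no higher than 17%, from an upper bound. The efficacy sentence reverses that logic. A cohort with three responses could then be reported as having shown a rate of 5% or less when the data show nothing of the kind.

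There is a related gap on the other side of the cut-off. The plan does not say what four or more responses would mean. Since 5% lies well below every response rate quoted above, a reader could take more from clearing the cut-off than it can carry.

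**Working it through.** **Inputs.** n = 30 per cohort, cut-off 3 or fewer, rates 5% and 20%, one-sided lower 80% bound (all section 8.3); comparison rates from 1.1.3.1 and 1.1.3.2.

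**Step 1: reproduce the plan's figures.** With X ~ Binomial(30, p):

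- p = 0.05: P(X ≤ 3) = 0.2146 + 0.3389 + 0.2586 + 0.1270 = 0.939. The plan says 94%.
- p = 0.20: P(X ≥ 4) = 1 − (0.0012 + 0.0093 + 0.0337 + 0.0785) = 0.877. The plan says 87%; 87.7% would round to 88%, which is immaterial.
- Exact (Clopper-Pearson) lower 80% bound at x of 30 = the 0.20 quantile of Beta(x, 31 − x). At x = 3 this is 5.16%, and Table 8.4 prints 5%. The table matches this formula in every row except 1/30 (exact 0.74%, printed 0%).

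So the method is identified and the arithmetic is sound.

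**Step 2: what 3/30 says about an upper limit.** The exact one-sided upper bound is the (1 − α) quantile of Beta(x + 1, 30 − x).

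| Responses of 30 | Observed | Lower 80% | Upper 80% | Upper 90% |
|---|---|---|---|---|
| 0 | 0.0% | 0.0% | 5.2% | 7.4% |
| 1 | 3.3% | 0.7% | 9.7% | 12.4% |
| 2 | 6.7% | 2.8% | 13.7% | 16.8% |
| 3 | 10.0% | 5.2% | 17.6% | 20.9% |
| 4 | 13.3% | 7.8% | 21.4% | 24.9% |

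Table 8.3, which is the same binomial calculation for DLTs, prints 21% for 3/30 at 90%. No row has an upper bound at or below 5%. For zero responses the 80% bound is 1 − 0.20^(1/30) = 5.2%.

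**Step 3: what the rule does support.** At a true 20%, P(X ≤ 3) = 1 − 0.877 = 12.3%. That is below the 20% error that the plan allows for efficacy, so three or fewer responses rules out a 20% rate at the one-sided 80% level. It does not at 90%, where the bound is 20.9%.

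**Step 4: what four or more responses supports.** The lower 80% bound is 5.16% at 3/30 and 7.75% at 4/30, so just clearing the cut-off excludes only rates up to about 5–8%. The chance of clearing it is:

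| True response rate | P(4 or more of 30) |
|---|---|
| 5% | 6.1% |
| 10% | 35.3% |
| 16.7% | 76.2% |
| 20% | 87.7% |
| 33% | 99.6% |
| 48% or more | above 99.9% |

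**Step 5: reach of Table 8.4.** Its last row, 12/30, has a lower bound of 31%. It therefore shows no bound near 48–65% or 59%. By the same formula, later rows would read 40.8% at 15/30, 50.6% at 18/30, 57.4% at 20/30 and 64.3% at 22/30.

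**The case against.** The best defence is that the rule is a coherent screen of 5% against 20%. Both stated probabilities reproduce, the level was deliberately relaxed, and the text calls the assessment preliminary and only suggestive. The efficacy objectives are to estimate and to summarise, with bounds reported whatever the count. All of that stands. It means that the design of the rule is not at fault and the consequences are modest. It does not rescue the phrase, because a relaxed level excuses a weak conclusion but not one pointing in the wrong direction.

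Three stronger readings are tempting, and the documents do not support them.

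- *The rule contradicts Table 8.4, because the bound at 3/30 exceeds 5%.* The excess is 0.16 percentage points in a table of whole percents, and at printed precision the two agree. The fault is the direction of the inference.
- *The plan would call a poor regimen promising.* It would not. The sentence is a one-way signal of lack of efficacy, and nothing declares success at four or more. The 76% in step 4 is the chance of not being flagged, not of a positive claim.
- *The plan should require a lower bound above the cited rates, for instance 8/30 (bound 19.1%) in Group 1 and 18/30 (50.6%) in Group 2.* Those benchmarks are selective. The 16.7% comes from 18 patients on immunotherapy alone (if 3/18, exact 95% interval 3.6–41.4%), while 59% is cited for symptomatic patients on targeted therapy and 33% for pre-treated brain metastases on encorafenib plus binimetinib. The brain rates are intracranial, whereas the response rate in section 8.2 is by RECIST. The 50% stratum was defined by LDH alone, while Group 2 also needs liver metastases or bulky disease. Such bars would also turn a futility screen into a superiority test: at a true 60% in Group 2, the chance of 18 or more of 30 is only 58%.

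**Conclusion.** The conclusion attached to three or fewer responses is wrong as written. At 3/30 the rate could be as high as 17.6% (80%) or 20.9% (90%), more than three times the ceiling stated. The operating characteristics stand, and so does the use of three or fewer as a suggestive futility signal. What needs correcting is one phrase, together with the missing statement of how little four or more responses shows.

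This rests on exact binomial bounds, which the printed tables imply, and on 30 evaluable patients per cohort. The synopsis makes Group 2 the remainder of 60, so its size need not be 30; the bounds would then shift, but a lower bound would still not support an upper-limit claim.

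**What to change.** In section 8.3, delete the clause about a rate of at most 5% and replace it with something like:

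> Three or fewer responses of 30 suggest lack of efficacy: at 3/30 the exact one-sided 80% upper bound is 17.6%, so a response rate of 20% is ruled out at that level.

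Keep the two stated probabilities (94% at 5%; 87.7% at 20%). Add a sentence that four or more responses excludes only a rate of about 5–8% and is not evidence of activity relative to the rates cited in the protocol (16.7% to 59% in symptomatic brain metastases, 48–65% with elevated LDH). Extend Table 8.4 beyond 12/30 so that bounds near those rates can be read.

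The cost is a text change and some table rows, with no effect on sample size, data collection or conduct. Whether to name a benchmark for activity, and which one, is for the sponsor to decide and justify.

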8.4 Proposed Analysis of Primary and Secondary Endpoints

Based on NCI Common Terminology Criteria for Adverse Events (CTCAE v5.0), the term toxicity is defined as AEs that are classified as either possibly, probably, or definitely related to study treatment. The maximum grade for each type of toxicity will be recorded for each patient, and frequency tables will be reviewed to determine toxicity patterns. The number of occurrences of each event will be tabulated by event and grade. In addition, the total number of patients experiencing AEs over their course of treatment will be characterized by type of AE and grade. For this summary grades will be grouped into Grade I/II vs III/IV. In addition, the number of patients experiencing a dose-limiting toxicity as defined in table 4.5.2 will be compiled. Inferences regarding recommended phase II regimen and safety in both phase I and phase II cohorts will be made by calculating the proportion of patients with a dose-limiting toxicity with a one sided upper 90% confidence bound.

For the phase II cohorts, both the objective response rate (complete or partial response) / total evaluable) and the clinical benefit rate (complete or partial response + stable disease / total evaluable) will be computed with lower 80% confidence bounds. Evaluable patients are those who got at least one dose of ipi/nivo. Progression-free survival will be estimated with 90% two-sided confidence intervals for each phase II cohort. For progression-free survival, an event is defined as disease-progression or death.

For exploratory biomarker analyses, Spearman's correlation will be used for continuous variables such as Ki67+, T cell-inflamed GEP, pathway enrichment scores, TMB and others. Wilcoxon rank-sum test will be used to compare TMB between groups. Fisher's exact test will be used to compare the fraction of mutated and non-mutated samples per gene and R vs NR between T cell-inflamed and non-inflamed groups. Recognizing RNAseq values are relative, we created a frozen reference set from TCGA using our previous work and bring newly collected samples to the same baseline by comparing to this reference. We transform new data into the reference set using linear regression and determining per sample T cell-inflamed score (>8.24; T cell-inflamed, <6.43; non-T cell-inflamed and others intermediate). Benjamini-Hochberg procedure will be used to control FDR from multiple comparisons. All tests will be two-sided.

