8.1 Objectives

Primary Objective

- To nominate a recommended phase II regimen (RP2R) of triple or quadruple therapy with encorafenib +/- binimetinib + nivolumab and + ipilimumab in *BRAF* mutated, metastatic melanoma.

Secondary Objectives

- To estimate the RECIST response rate of triple or quadruple therapy in high risk populations of *BRAF* mutated, metastatic melanoma.
- To estimate the CNS clinical benefit rate (CBR, defined as complete response [CR] + partial response [PR] + stable disease [SD] >6 months) per RANO-MB criteria of triple or quadruple therapy in *BRAF* mutated, metastatic melanoma to the CNS
- To describe the toxicity, by CTCAEv5, of triple or quadruple therapy in *BRAF* mutated, metastatic melanoma
- To summarize the progression-free survival of triple or quadruple therapy in high risk populations of *BRAF* mutated, metastatic melanoma

Exploratory Objectives

6. To evaluate association between treatment response and baseline tumor mutational burden, changes in the tumor microenvironment (IFN associated gene expression), T cell clonality, and other biospecimens before and after triple or quadruple therapy.

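### Section 8.4 names only a two-group Fisher test for response against the continuous T cell-inflamed score, with no place for intermediate patients; a rank test on all scored patients would be more sensitive if response varies smoothly with the score

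*Combined protocol and SAP*

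**What the plan says.** Section 8.4 derives a T cell-inflamed score for each sample against a fixed TCGA reference and sorts samples into three groups: ">8.24; T cell-inflamed, <6.43; non-T cell-inflamed and others intermediate". It then applies Fisher's exact test to two comparisons: mutated against non-mutated samples per gene, and "R vs NR between T cell-inflamed and non-inflamed groups". Only two of the three score groups appear in the second comparison, and the paragraph gives no handling for the third.

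The same paragraph contains these related statements:

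- Spearman's "correlation will be used for continuous variables such as Ki67+, T cell-inflamed GEP, pathway enrichment scores, TMB and others". The variable paired with these is not stated.
- "Wilcoxon rank-sum test will be used to compare TMB between groups". The groups are not defined.
- "Benjamini-Hochberg procedure will be used to control FDR from multiple comparisons". No FDR level is given.
- "All tests will be two-sided".

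The objective served is exploratory. Section 8.1 reads "To evaluate association between treatment response and baseline tumor mutational burden, changes in the tumor microenvironment (IFN associated gene expression" and goes on to other specimens. The plan states no power, effect size, response rate by score or expected intermediate share for this analysis.

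**The concern.** The score is measured on a continuous scale, yet the named response test uses only whether it falls above one cut or below another. Information is lost in two ways: intermediate patients contribute nothing, and differences within each outer group are ignored.

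Tissue is scarce. Inclusion criterion 5 (section 3.3.1) asks for fresh biopsies from ten patients in each Phase I cohort, and section 5.4 limits fresh biopsy to Phase I. Archival tissue is required only if available. The analysis may therefore rest on about 20 patients. Sections 1.1.3 and 1.1.4 use the low expression/low mutational burden group as part of the case for adding CTLA-4 blockade, so a real association missed here would be a loss to the translational part of the study. Silence about intermediates also leaves open, until the data are seen, who enters the test.

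**Working it through.** **No stated figure to reproduce.** The plan gives no power for this analysis, so the check compares the planned test with an alternative under stated assumptions.

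**Inputs from the documents**

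- Cuts at 8.24 and 6.43, Fisher's exact test, two-sided tests (section 8.4).
- Fresh tissue: 2 cohorts × 10 = 20 patients (section 3.3.1).
- Upper limit if every patient had usable tissue: "The total enrollment, in the absence of early stopping, is 84 patients (24 phase I / 60 phase II").

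**Assumptions, none of them in the documents**

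- Nominal two-sided 5% per test, before FDR control.
- Intermediate share 20%, 33% or 50%.
- Model A: score normal with SD 1 within responders and non-responders, means 0.8 or 1.0 SD apart, response 40% or 60%.
- Model B: score x standard normal, P(response | x) = 1 / (1 + exp(−(a + x·ln OR))), with OR 2-3 per SD and overall response 30% or 50%.

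**Tests compared**

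- Planned: two-sided Fisher's exact p on the 2×2 table of response by outer group, intermediates not used. At n = 20 with one third intermediate, about 20 × 2/3 ≈ 13 patients remain.
- Alternative: Wilcoxon on all n. With U the rank-sum statistic for the n1 responders against the n0 non-responders, z = (|U − n1·n0/2| − 0.5) / √(n1·n0·(n+1)/12).

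Each setting used 3,000-4,000 simulated trials. The standard error of one power estimate is at most √(0.25/3000) ≈ 0.9 points.

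**Model A (smooth), ranges over the settings**

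| n | Fisher, outer groups | Wilcoxon, all | Gain (points) |
|---|---|---|---|
| 20 | 15-33% | 32-49% | 12-24 |
| 40 | 45-68% | 63-83% | 13-19 |
| 60 | 67-87% | 82-95% | about 8-16 |

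For example, at n = 20 with a 1.0 SD difference, 40% response and one third intermediate: 46.0% − 28.1% = 17.9 points. At n = 84 the gain is 8-10 points at 0.8 SD and about 3 at 1.0 SD.

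**Model B (smooth), 33% intermediate, 30% response**

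| n | OR 2: Wilcoxon vs Fisher | OR 3: Wilcoxon vs Fisher |
|---|---|---|
| 20 | 20% vs 9% | 40% vs 21% |
| 30 | 32% vs 19% | 61% vs 42% |
| 60 | 60% vs 45% | 91% vs 81% |

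Over OR 2-3, all three intermediate shares, both response rates and n = 20, 30 and 60, the gain is 7.7-23.8 points.

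**How far the figure moves with the assumptions**

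- Balanced cuts, n = 20-60: OR 1.5 gives 4-10 points; OR 4 gives about 3-30.
- Unequal outer groups (such as 20% low and 40% high), OR 2-3: 9-29 points.
- Response flat within each third and changing only at the cut-points: 5-9 points at n = 20, 1-9 at n = 30 and −1 to 3 at n = 60. With response 20/40/60% across the thirds, for example, Wilcoxon against Fisher is 25.0% vs 18.7% at n = 20 and 67.0% vs 67.2% at n = 60.

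**Where the loss comes from** (n = 20, OR 3, 30% in each outer group)

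- Continuous score, all patients: 45.7%.
- Continuous score, intermediates dropped: 34.7%, a loss of 11.0 points.
- Fisher on the two groups: 26.6%, a further loss of 8.1 points.

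Part of the second loss reflects Fisher's conservatism. With no association, 40% response and one third intermediate, its actual size is 1.7% at n = 20, 2.7% at n = 30 and 3.0% at n = 60, against 4.5%, 4.5% and 4.7% for Wilcoxon.

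**The case against.** The strongest reply is that a continuous analysis may already be intended. Spearman's correlation is listed for the T cell-inflamed score, and section 1.3 words the exploratory objective as response correlated with these markers. For a binary response and an untied score, the Wilcoxon statistic without continuity correction is z = ρ·√(n−1), so Spearman with response is essentially the test recommended here. In simulation (40% response, one third intermediate), Fisher, Wilcoxon and Spearman had power 30%, 48% and 51% at n = 20 with a 1.0 SD difference, and 46%, 62% and 63% at n = 40 with 0.8 SD. This reading is plausible, but section 8.4 never names response as Spearman's partner, while it does assign responders against non-responders to Fisher.

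Second, the cuts are fixed in advance, and the rationale in sections 1.1.3 and 1.1.4 is framed in high and low categories. A comparison of those categories is a legitimate question. That stands, and it is why the category table should stay.

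Third, the treatment of TMB is a weak precedent. The groups in that Wilcoxon comparison are undefined and need not be responders and non-responders. The FDR adjustment does not favour either option, since it applies to both.

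Fourth, even the better test has only 32-49% power at n = 20 under Model A. The change improves a weak analysis without making it conclusive.

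**Conclusion.** The point holds as a minor improvement to an exploratory analysis. The one test explicitly named for response against the score uses two cut groups and gives intermediates no role. The cost is about 8-24 points of power at n = 20-60, provided response varies smoothly with the score at a moderate effect (0.8-1.0 SD, or OR 2-3 per SD) and 20-50% of patients are intermediate. It is about 4-10 points at OR 1.5. If response steps exactly at the cut-points, it is about 5-9 points at n = 20 and near zero at n = 60.

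Three stronger readings are tempting, and the documents do not support them:

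- That 8-24 points is a general figure. The effect size, response shape and intermediate share behind it are all assumed, and the number with usable tissue is unknown.
- That the plan expressly excludes intermediates, or uses the score only in cut form. Exclusion is inferred from the two groups named, and Spearman is listed for the score.
- That the trial's conclusions are at risk. Regimen selection, toxicity monitoring and the primary and secondary endpoints do not use this test.

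**What to change.** In section 8.4, state that response will be tested against the continuous T cell-inflamed score by the Wilcoxon rank-sum test in all patients with a sample, including intermediates. Alternatively, name response as the variable paired with the score in the Spearman analysis, which is nearly equivalent. Keep the inflamed / intermediate / non-inflamed by response table as a descriptive display, and keep Fisher's exact test for the per-gene mutation comparisons, where the data are binary.

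The cost is a sentence or two. No new data are needed, because the score is already computed per sample. There is a small downside: the formal test no longer targets the pre-set categories directly, and if response truly steps at the cut-points about one point of power at most is given up (seen at n = 60, and of the order of simulation error).
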